Research Protocol

Randomised controlled trial on the efficacy of Audio-visual Health Educational materials on CPAP ADherence: The ADHEAD trial

Principle Investigators:

[name], MBChB, Sleep medicine advanced trainee
Department of Respiratory and Sleep Medicine, Princess Alexandra Hospital
Email: [contact]. [contact]

[name], BSc, MBBS, FRACP, Respiratory and Sleep Physician
Department of Respiratory and Sleep Medicine, Princess Alexandra Hospital
Email: [contact]. [contact]

[name], Scientific Director
Sleep Disorders Centre, Princess Alexandra Hospital
Email: [contact]. [contact]

INTRODUCTION

Sleep disorders, particularly obstructive sleep apnoea (OSA) are common conditions amongst the Australian adult population; over 10% of Australian men over aged 45 years have OSA and associated symptoms¹. OSA is clinically defined as repeated episodes of obstruction of the upper airways during sleep resulting in sleep fragmentation, non-restorative sleep and daytime symptoms such as increased daytime sleepiness, daytime napping and poor mood. As such, sleep disorders are associated with significant cost burden to the Australian economy; OSA is estimated to cost \$2.6 billion annually through lost productivity, mortality and absenteeism¹. Of great significance is the 2-3 fold increase in all-cause mortality amongst individuals with severe untreated OSA¹.

The treatment of choice for moderate to severe OSA is continuous positive airway pressure (CPAP)². By producing a continuous flow of positive airway pressure via a mask, airways that would otherwise obstruct in OSA remain patent. CPAP treatment has a well-established benefit in improving daytime somnolence, motor vehicle accidents risk and quality of life. Compliance with CPAP therapy however remains a challenge for many sleep physicians and their patients. Adherence to the recommended 4 hours or more a night on CPAP amongst individuals with OSA ranges from 40-60%³. CPAP compliance success depends on the balance between symptoms, perceived risks of negative outcomes, perceived barriers and perceived benefits³. Many of these factors can be optimised through patient education.

Health Literacy is a multifaceted concept defined as 'The degree to which individuals have the capacity to obtain, process and understand basic health information and services needed to make appropriate health decisions⁴. In the USA it is estimated that only a third of adults have basic health literacy⁴ and similarly only about 40% of adult Australian's have adequate health literacy⁵. Low individual health literacy is associated with higher rates of hospitalisation, emergency care, and adverse health outcomes⁶.

A recent pilot project was conducted at the Princess Alexandra Hospital in 2018 to evaluate the Health Literacy of our Sleep Disorders Clinic patients. The results of this pilot study demonstrated in a sample of 101 patients using internationally validated questionnaires, 28% had inadequate health literacy and 37% had no further education beyond grade 10 (unpublished data). Of our cohort, 40% reported they do not always feel confident completing medical forms, and 31% do not always feel confident reading medical information themselves. These results are in keeping with the only other available Australian data⁶.

Within the pilot project performed at the Sleep Disorders Clinic at Princess Alexandra Hospital, a needs analysis was included. This questionnaire asked patients their preferred method of health education delivery. A total of 64% of the 101 patients who participated reported they would like health information regarding their sleep disorder to be made available in an online video format. Similarly 64% reported that they can easily access video streaming sites such as Youtube® and 79% of our cohort reported having access to the Internet at home or on a mobile device (unpublished data).

With this information, a novel idea has been formed to evaluate whether the development and implementation of audio-visual health information can improve the sleep-specific health literacy and CPAP usage in our Sleep

Disorders Clinic patients. There have been very few trials in this area previously and thus far with negative results⁷. This novel study aims to for the first time in an Australian setting, randomise patients to an intervention group who watch audio-visual sleep health information or standard of care, for the first time in an Australian setting. CPAP adherence and health literacy will be evaluated to assess the effect-~~efficacy~~ of the new informational style in improving sleep related health outcomes.

RESEARCH QUESTION

Does additional health information delivered with audio-visual videos improve CPAP uptake and adherence in patients with OSA?

HYPOTHESIS

Delivery of health information with audio-visual sleep health information in the form of five video clips will improve CPAP uptake and adherence in patients with OSA.

STUDY AIM

This study aims to determine whether audio-visual sleep health information in the form of five video clips improves CPAP uptake and adherence in patients who attend a public sleep disorders clinic.

Aim 1 – To compare the CPAP uptake of patients who have watched sleep educational materials compared with standard of care over a 2-month and 12-month period.

Aim 2 – To compare the CPAP adherence of patients who have watched sleep educational materials compared with standard of care over a 2-month and 12-month period.

INTERVENTION

Five short audio-visual clips have been developed by the Department of Respiratory and Sleep

Medicine.

Video	Topic and general content
1 – About Obstructive obstructive Sleep-sleep apnoea	Introduction to the symptoms, initial consultation with GP and referral process to sleep specialist services
2 – About the sleep study	Review of the preparation needed for attending a sleep study and what is involved
3 – Accessing the Qld Health Sleep Disorders Program	Requirements and processes for qualifying for a Queensland Government funded CPAP machine
4 – What is CPAP and how does it work	Discussion of the indications, benefits and pitfalls of CPAP therapy
5 – CPAP trouble shooting	How to care for your equipment and what-how to do-deal with common device troubles such as mask leak

METHODS

Study Design: A prospective randomised control trial will be performed.

Participants and setting:

The Sleep Disorders Centre (SDC) holds multiple sleep medicine clinics that occurs in the 2F Respiratory and Sleep Medicine outpatient department at Princess Alexandra Hospital (PAH). Patients are referred from primary care physicians or other medical specialists drawing from a vast geographic catchment throughout Queensland and northern New South Wales. The clinic averages an attendance of ~45 patients per week and is run 45 weeks of the year.

Recruitment:

All treatment naïve new case sleep patients attending the SDC will be invited to participate. The sleep laboratory administration staff will send out a study information flyer with the standard appointment confirmation letters. This flyer will invite treatment naïve new case patients to participate in the study. Patients interested will be invited to participate at the end of their initial sleep consultation and provided the Patient Information and Consent Form (PICF) to take home and consider. Additionally as part of the standard telephone confirmation process prior to upcoming sleep studies, sleep laboratory administration staff will offer the option of participation in the trial. Within the sleep database their details will be added to the research participation log.

Study procedure:

When eligible patients return to the sleep laboratory for their CPAP initiation sleep study, consent will be obtained by a research sleep scientist appointed as part of the study. At this point participating patients will be randomised to either Group 1 "Standard of care" or Group 2 "audio-visual clips". Sealed envelopes containing cards method will be used. Equal number of cards for each arm will be placed in opaque envelopes. The envelopes will be placed in a box in a locked cupboard in the sleep laboratory. An independent staff member of sleep laboratory will pick an envelope after consenting the patient.

For patients in Group 1 "Standard of Care" education will be provided at night by the sleep scientists according to standard laboratory policy and procedures. This includes a two-page written patient handout about the study and OSA. The following morning, a sleep physician will review the patient's data and counsel them on the results to implement a management plan (as per standard of care).

For those participants in Group 2 "Audio-visual clips" following their usual sleep study set up, with education from the night sleep scientific staff, a computer will be provided with Video 1 and Video 2 loaded, with assistance from the sleep scientists to play the video. The following morning, the reviewing Sleep Physician will perform data and interventions as standard of care. The participating patients s will stay in the laboratory for an additional 20 minutes to watch video 3, 4 and 5.

As standard of care, participants from both arms will return to the laboratory and outpatient clinic at 2 months and 12 months following their studies for review of their CPAP machine. At these times CPAP uptake and adherence and Epworth Sleepiness Score questionnaire will be collected, as standard of care in both arms.

Inclusion and exclusion criteria:

Inclusion criteria

- All treatment naïve patients attending Sleep Disorders Clinic for sleep studies with suspected or proven obstructive sleep apnoea who able to provide informed consent.
- Adult patients (18 years and older).

Exclusion criteria

- Those unable to provide informed consent.
- Patients from non-English speaking background, as video clips will only be provided in English initially.
- Patients less than 18 years old.

Power calculation:

Previous studies have estimated a sample size of 200 patients are required to detect a 1 hour per night increase in CPAP adherence. Assuming an SD of 2.5 hours based on previous observational data and power of 80%, with a two-sided significance level of 0.05, the estimated total sample size is 208 patients¹¹.

End points:

Primary Outcome

The primary outcome of this study is to determine CPAP adherence (hrs) in both standard of care and audio-visual arms at 2-months and 12-months. CPAP counter metres are present in all modern CPAP devices. This is a tamper-proof method whereby machine usage hours are detected by in-device computers and is usually downloaded at clinic follow up.

Secondary Outcomes

- Non-scheduled sleep scientist time (phone calls and clinic consultation) measured in minutes. The Sleep Disorders staff at the Princess Alexandra Hospital already routinely collects this information via the Sleep Disorders database. The Study Co-ordinator will obtain this from the sleep database at 2-months and 12-months.
- CPAP therapy uptake at 2-months and 12-months.

Data collection

Data collection method and storage

A research sleep scientist and the principal investigator [name] will carry out all data collection. All data collected will be de-identified and no personal details of patients will be collected as part of this study.

Data will be collected on to a Microsoft Excel file which will be password protected. The collected data will be stored on a secure Queensland Health computer located at the Department of Respiratory and Sleep Medicine at Princess Alexandra Hospital.

As per the requirements stated in the Australian Code for the Responsible Conduct of Research, the data will be securely stored for 15 years from the date of completion of the project. If the principle investigator moves on from Queensland Health in that time period, access to the data will be provided to the senior associate investigator.

Data variables

Both groups will have demographic data and a number of internationally validated questionnaires (Epworth Sleepiness Score, quality of life questionnaires, insomnia questionnaires and depression questionnaires) and OSA diagnostic information collected at recruitment and the follow-up periods as outlined above; all of which is current standard of care. CPAP uptake and adherence data will also be downloaded from the CPAP machine and entered into the Sleep Disorders database as per usual practice, and collected as part of the study at the follow-up times.

Analysis

Statistical analysis plan:

The analysis will be carried out on an intention-to-treat principle. Estimated frequencies and proportions for the variables will be calculated in descriptive analysis. The Chi-Squared test will be used to compare the rates and t-test to compare means. The threshold for statistical significance will be established at 5%. Data quality will be assessed after data collection and potentially inform the analytical methods. The analyses will be carried out using Statistical Package for the Social Sciences version 24 (SPSS for Windows, IBM Corporation, Somers, NY, USA).

RISKS

There are no extra risks or disadvantages to patients by taking part in this study. Patients may be requested to stay an extra 30 minutes after their sleep study to watch the videos and complete a questionnaire. Rest of the management is all part of standard care.

TIMELINE

Expected start date: April 2019

Recruitment phase: 12 months

Expected completion date: April 2020

RESEARCH OUTPUTS

Results of this study will predominantly be distributed to the clinical staff involved in immediate care of patients with obstructive sleep apnoea through departmental presentations and internal reports. The results may also be presented at conferences and published in peer reviewed journals relevant to the field.

REFERENCES

1. Reawakening Australia: The economic cost of sleep disorders in Australia. . Sleep Health Foundation, 2011. (Accessed September 2015, at http://www.sleephealthfoundation.org.au/pdfs/news/Reawakening_Australia.pdf.)

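### The envelope is drawn at consent, before the standard night education, although nothing specific to an arm is needed until that education is over; it should stay sealed until then

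*Protocol*

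**What the plan says.** All of this is in the Protocol, Study procedure.

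- **Randomisation.** Consent is obtained when the patient returns for the CPAP initiation study: "At this point participating patients will be randomised to either Group 1" or Group 2. On the draw: "An independent staff member of sleep laboratory will pick an envelope after consenting the patient".
- **Night care, Group 1.** "education will be provided at night by the sleep scientists according to standard laboratory policy and procedures", including a two-page handout on the study and OSA.
- **Night care, Group 2.** "following their usual sleep study set up, with education from the night sleep scientific staff, a computer will be provided" with the first two videos loaded, "with assistance from the sleep scientists to play the video".
- **Next morning.** In Group 1 the physician is to review the data and "counsel them on the results to implement a management plan". In Group 2 the physician's review is likewise described as standard care. After describing it, the text says that these patients "will stay in the laboratory for an additional 20 minutes to watch video 3, 4 and 5".

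No sentence says to whom the allocation is disclosed, when the envelope is opened, or that the scientists or the physician are kept unaware of it.

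**The concern.** The Research Question asks what additional information by video achieves. That contrast needs the standard education underneath it to be the same in both arms. Under the sequence described, the arm can be known before that education starts.

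The temptation to vary it is plausible because the content overlaps. The standard handout covers the study and OSA, and Videos 1 and 2 cover OSA and the sleep study (Intervention table). A scientist who knows that a patient will shortly watch those videos might shorten the talk, or might do more for a patient who will not. The former would tend to understate the additional effect of the videos, as would the latter. Enthusiasm for materials made by the same department could work the other way. Whatever the direction, the estimate would be the videos plus a change in usual care.

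Device-recorded hours protect how the outcome is measured. They do not protect the equality of the care given before it.

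**Working it through.** **1. Order of steps in Study procedure**

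| Step | Group 1 | Group 2 | Is the arm needed to deliver it? |
|---|---|---|---|
| Consent, randomisation, envelope draw | yes | yes | – |
| Set-up and night education | standard | standard | no |
| Videos 1 and 2 | – | after education, scientists assist | yes |
| Morning physician review | standard | standard | no |
| Videos 3 to 5 | – | described after the review | yes |

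The draw stands one step earlier than the allocation is needed. For the night education, full concealment is possible because nothing has yet happened that differs by arm. For the physician it is not, because Group 2 has watched two videos the night before.

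**2. The plan's own sample size**

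Inputs (Protocol, Power calculation): difference 1 h per night, SD 2.5 h, power 80%, two-sided 5%. Equal allocation is from Study procedure.

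- Normal approximation: n per arm = 2 × (1.960 + 0.842)² × 2.5² / 1² = 98.1, so 99 per arm and 198 in total.
- With the t-distribution: 99.08, so 100 per arm and 200 in total.

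This matches the 200 given in the same section. The stated 208 is slightly larger and would fit an unstated 5% allowance (198 × 1.05 = 207.9). Power at 208 is 82%. The figure is mildly conservative and does not affect this point.

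**3. What unequal usual care could do (assumed values)**

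The Protocol gives no figure for a difference in usual care, so b, its effect in hours per night, is assumed over a range. All 208 patients are taken as analysed.

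- SE of the difference = 2.5 × √(2/104) = 0.347 h.
- If the videos have no effect, rejection rate = 1 − Φ(1.96 − b/SE) + Φ(−1.96 − b/SE).

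| b (h per night) | b/SE | Rejection rate |
|---|---|---|
| 0 | 0 | 5.0% |
| 0.1 | 0.29 | 6.0% |
| 0.25 | 0.72 | 11.1% |
| 0.5 | 1.44 | 30.3% |

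Bias can also hide an effect. If the videos truly add 1 h but controls receive extra education worth an assumed 0.25 h, the expected difference is 0.75 h, z = 0.75/0.347 = 2.16, and power is about Φ(2.16 − 1.96) = 58% instead of 82%.

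These figures show how the test would respond. They are not evidence that such a difference will occur.

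**The case against.** The strongest reply is that the Protocol does not say that the scientists know the arm. It says that an independent staff member picks an envelope. The scientists' only task specific to an arm is helping to play the videos, which follows education. This stands: a reader might infer that staff educate in full knowledge of the allocation, but the text supports only that nothing prevents it.

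Second, the Protocol ties education to laboratory policy, and the physician's part to standard care, in both arms. This is a real safeguard of intent. But education and counselling are spoken and can vary in length and emphasis, and no script or check is described.

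Third, concealment from the physician is not free. Patients may mention Videos 1 and 2. The place of Videos 3 to 5 after the review is the order of the narrative rather than a stated rule; the Risks section says only that patients may stay an extra 30 minutes after the study. This also stands, and it makes the physician's part secondary. Nor do the documents say that counselling decides CPAP uptake; they say that it serves a management plan.

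Fourth, the gain is partial. Follow-up visits run to 12 months, and unscheduled scientist contacts are a secondary outcome. Staff at those contacts remain unblinded. This is correct, but it is no reason to leave open the one step that can be closed almost freely.

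Finally, randomising at consent in an open educational trial is workable. That is true, which is why this is an improvement to a stated sequence and not a fatal flaw.

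**Conclusion.** The point holds for the sequence. Randomisation and the draw come before the standard night education, the allocation is not needed until that education is complete, and nothing keeps it from those who educate. That exposes the comparison of added video information to unequal usual care which could be avoided.

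The size and direction of any bias cannot be derived from the Protocol. Rejection rates of about 6%, 11% and 30% under no video effect rest on assumed differences of 0.1, 0.25 and 0.5 h per night, the Protocol's SD of 2.5 h and 104 analysed per arm.

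Two stronger readings are not supported. One is that staff will treat the arms differently: their knowledge of the arm is itself inferred, and unequal care is a risk, not a finding. The other is that all usual care could be given blind at no cost: that is close to true for the night education, but not for the morning counselling.

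**What to change.** - Keep consent on arrival and let the independent staff member draw the envelope as planned. State that it stays sealed until set-up and standard education are complete, and is opened just before Video 1 would start. Because the draw does not move, its independence is kept and that person need not be present later.
- Record the time at which education ended and the time at which the envelope was opened, so that the order can be checked.
- As a secondary and partial measure, state that the allocation is not disclosed to the reviewing physician before the morning counselling, and that Videos 3 to 5 follow that review.
- State in the Protocol who is told the allocation and when.

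Cost: a small logistic change on the night and a line or two of record keeping. The sample size does not change, and neither does the content of care. What remains is imperfect blinding of the physician, because patients may mention the videos, and unblinded contacts during follow-up. The report should acknowledge both.

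### CPAP adherence at 2 and 12 months is the primary outcome with neither visit ranked and no decision rule, while the sample size covers one comparison tied to no visit

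*Protocol*

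**What the plan says.** **Outcome.** Under End points, Primary Outcome, the Protocol sets out to "determine CPAP adherence (hrs) in both standard of care and audio-visual arms at 2-months and 12-months". Aim 2 under Study Aim likewise names both periods: "To compare the CPAP adherence of patients who have watched sleep educational materials compared with standard of care over a 2-month and 12-month period". Neither place puts one visit ahead of the other.

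**Analysis.** The Analysis section states "The Chi-Squared test will be used to compare the rates and t-test to compare means", and "The threshold for statistical significance will be established at 5" per cent. It gives no order of testing, no division of the 5%, and no rule on whether one or both visits must be positive. It also lets data quality, assessed after collection, influence the methods.

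**Sample size.** The Power calculation cites earlier work in which "a sample size of 200 patients are required to detect a 1 hour per night increase in CPAP adherence", then continues "Assuming an SD of 2.5 hours based on previous observational data" with 80% power and, "with a two-sided significance level of 0.05, the estimated total sample size is 208 patients". The effect, the SD and the number of patients are attached to no visit.

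**Timeline.** Start is expected in April 2019, recruitment lasts 12 months, and completion is expected in April 2020.

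**The concern.** The primary outcome yields two between-arm comparisons of mean hours, and the only threshold available for each is 5%. The trial is sized as if there were one comparison. Which error rate and power apply then depends on a rule that the Protocol does not give.

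- If a positive result at either visit is enough, the chance of a false claim exceeds the stated 5%.
- If both visits must be positive, the chance of success falls below the stated 80%.
- If the visits disagree, the trial has no predefined primary answer, and the visit to emphasise could be chosen after the results are seen.

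**Working it through.** **Inputs from the Protocol.** Difference 1 h, SD 2.5 h (standardised difference 0.4), two-sided 0.05, power 80%, total 208 (Power calculation); 1:1 allocation, from "Equal number of cards for each arm will be placed in opaque envelopes" (Study procedure); t-test for means (Analysis). With equal arms there are 104 patients per arm.

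**Assumed, because the Protocol does not give it.** The correlation ρ between the two visits' test statistics, shown from 0 to 0.9. For power, a true 1 h difference and an SD of 2.5 h at both visits, with all 208 patients analysed.

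**1. The Protocol's own figures.** The normal approximation gives n per arm = 2 × (1.960 + 0.842)² × 2.5² / 1² = 98.1, so 99 per arm and 198 in total. The t-test needs 99.08, so 100 per arm and 200 in total, which reproduces the 200 quoted. The 208 is 8 to 10 patients above this, a small allowance that the Protocol does not explain. With 104 per arm, the t-test has 81.9% power (normal approximation 82.2%). So 208 fits one two-sided 0.05 comparison.

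**2. Either visit suffices, each at 5%.** False-positive rate = 1 − P(|Z₁| ≤ 1.96 and |Z₂| ≤ 1.96), with (Z₁, Z₂) bivariate normal with correlation ρ. For ρ = 0 this is 1 − 0.95² = 0.0975.

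**3. Both visits required.** The expected test statistic at each visit is 1 / (2.5 × √(2/104)) = 0.4 × √52 = 2.884. Joint power = P(Z₁ > 1.96 and Z₂ > 1.96) with both means 2.884. For ρ = 0 this is 0.8224² = 0.6763.

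**4. Either visit suffices, Bonferroni at 0.025 each.** Power at one visit is 73.4% (t-test; normal approximation 74.0%). For at least one success with ρ = 0, power is 1 − (1 − 0.7399)² = 0.932.

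| ρ | False-positive rate, either visit at 5% | Power, both required | Power, at least one, each at 5% | Power, at least one, Bonferroni |
|---|---|---|---|---|
| 0 | 0.0975 | 0.6763 | 0.9685 | 0.9323 |
| 0.5 | 0.0907 | 0.7183 | 0.9265 | 0.8726 |
| 0.7 | 0.0835 | 0.7418 | 0.9030 | 0.8417 |
| 0.8 | 0.0781 | 0.7566 | 0.8882 | 0.8226 |
| 0.9 | 0.0704 | 0.7759 | 0.8689 | 0.7981 |

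**5. Patients needed for 80%.** If both visits are required: 258 (ρ = 0), 246 (0.5), 230 (0.8) or 220 (0.9). For 80% at each visit under Bonferroni: 238 by the normal approximation, 242 by the t-test.

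**6. Timeline.** A patient enrolled in month m after April 2019 reaches the 12-month visit in month m + 12. Completion in April 2020 is month 12. If that date means the end of the study, only patients enrolled at the very start could have a 12-month visit by then.

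**The case against.** **The error rate is conditional.** A reader might infer that the trial's false-positive rate simply is 8% to 9%. The documents do not support that. It requires that either visit counts as success and that ρ lies between roughly 0.53 and 0.77, and the Protocol states neither. If both visits must be positive, the rate cannot exceed 5%. Aim 2 speaks of adherence over each period; if the 12-month figure is cumulative it contains the first two months, which would raise ρ and reduce the inflation. This objection stands. What can be said is up to 9.75%, depending on rule and correlation.

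**The power statement is not wrong on every reading.** A reader might also infer that 208 patients are too few whichever rule applies. They are not. If either visit suffices, power for at least one success at ρ from 0.8 to 0.5 is 89% to 93% unadjusted and 82% to 87% with Bonferroni, and still about 80% with Bonferroni at ρ = 0.9. The 73% under Bonferroni is power at one given visit, not for the trial. This also stands.

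**Testing each visit at 5% is an inference, and a separate statistical analysis plan may exist.** Testing order and adjustment are often left to such a plan, so their absence from the Protocol is not the point here. Which visit defines the primary outcome is a Protocol matter. The Protocol names two, ranks neither and ties its sample size to neither. The 5% reading is the natural one, since no other threshold is given.

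**Conclusion.** The point holds in conditional form. What is certain from the Protocol is that two unranked visits share the primary outcome, no rule says whether one or both must be positive, and the sample size is for a single comparison with no visit attached.

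The size of the problem depends on the missing rule. If either visit suffices at 5%, the false-positive rate is 9.1% to 7.8% for ρ from 0.5 to 0.8, and at most 9.75%. If both are required, power is about 72% to 76% over the same range, some 4 to 8 points below the stated 80%, with no inflation. If one visit is named, power is about 82% and the stated design works. These power figures assume a 1 h effect and an SD of 2.5 h at each visit that is tested, and no losses; ρ is assumed throughout.

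The documents contain no data on completeness of follow-up or on change in CPAP use over time, so they do not themselves favour either visit on those grounds. The stated timeline does bear on whether 12 months is feasible. Because this governs the trial's main conclusion, it should be settled before any comparative data are seen.

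**What to change.** 1. **End points:** name one primary time point for mean hours of CPAP use, and make the other visit the first secondary outcome.
2. **Analysis:** test the primary visit at two-sided 5%, and the other at 5% only if the first is significant. This fixed sequence holds the overall error for the two visits at 5% without splitting it.
3. **Power calculation:** state that the 1 h effect, the 2.5 h SD and the 208 patients refer to the named visit.
4. **Timeline:** if 12 months is chosen, first reconcile the April 2020 completion date with 12 months of recruitment followed by 12 months of follow-up.

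The cost is a sentence in each section concerned. No extra patients are needed for the primary test, since 208 gives 81.9% power at one visit. The downside is that the second visit can be claimed only if the first succeeds. If the sponsor prefers to keep two primary visits, the Protocol should state the rule and the alpha for each, with the sample size reworked to match: for example 230 to 246 patients if both are required and ρ is 0.8 to 0.5.

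### The primary outcome has no stated value for randomised patients without a CPAP machine or download, so the intention-to-treat comparison is not secured

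*Protocol*

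**What the plan says.** - **Analysis principle and test** (Protocol, Analysis, Statistical analysis plan): "The analysis will be carried out on an intention-to-treat principle". Rates are compared by chi-squared test and means by t-test. The same paragraph lets an assessment of data quality, made after collection, shape the methods.
- **Primary outcome** (End points, Primary Outcome): CPAP adherence in hours, in both arms, at 2 and 12 months. On its source, the section says that "machine usage hours are detected by in-device computers and is usually downloaded at clinic follow up". Data variables names the same source, the machine, for both uptake and adherence. The endpoint has no denominator and no time window, although the power calculation is per night.
- **Uptake** (Secondary Outcomes): a separate endpoint, "CPAP therapy uptake at 2-months and 12-months". The Hypothesis expects the videos to improve it, and Video 3 explains how to qualify for a publicly funded machine.
- **Timing** (Study procedure): randomisation takes place at the CPAP initiation sleep study, before uptake at home is known. The inclusion criteria admit suspected as well as proven OSA.
- **Aim 2** (Study Aim): to "compare the CPAP adherence of patients who have watched sleep educational materials compared with standard of care".
- **Sample size** (Power calculation): 208 patients in total, with 80% power. No allowance for non-uptake or missing downloads is stated.

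**The concern.** Whether a patient has a machine is settled after randomisation, and the videos are meant to influence it. A t-test uses only patients who have a value. If hours come only from machines, a patient who never obtains one contributes nothing, and the comparison is then conditioned on a consequence of the intervention.

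This can mislead in a specific way. Suppose the videos bring in patients who would otherwise have declined, and those patients use CPAP less than the average user. The mean among users then falls in the video arm while that arm as a whole uses CPAP more. If the extra users are typical, a real gain made through uptake disappears from the primary comparison.

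Two situations need to be kept apart. A patient known to have declined or never obtained CPAP has a true value of 0 h. A patient with a machine but no download has an unknown value.

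**Working it through.** **1. The plan's own figure.** The inputs from Power calculation are "detect a 1 hour per night increase in CPAP adherence", "Assuming an SD of 2.5 hours based on previous observational data", 80% power and a test "with a two-sided significance level of 0.05". Allocation is equal (Study procedure: "Equal number of cards for each arm will be placed in opaque envelopes").

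- Normal approximation: n per arm = 2 × (1.960 + 0.842)² × 2.5² / 1² = 98.1, rounded up to 99, or 198 in total.
- Exact t-test: 99.08 per arm, rounded up to 100, or 200 in total. This matches the other figure in that section.
- The stated 208 is 10 more than 198, about 5%, by a step that is not explained. Power at 104 per arm is 82.2%. The surplus is on the safe side and is not the issue here.

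**2. Who has a value.** Taking the sections in order: randomise at the initiation study; uptake follows; hours are read from the machine; means are compared by t-test. No sentence assigns hours to a randomised patient with no machine.

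**3. All randomised against users only.** The documents give no uptake rate and no mean hours among users, so the inputs below are assumptions. Let p_C and p_V be uptake in the control and video arms, m the mean hours of patients who would take up CPAP anyway (assumed unaffected by the videos), and e the mean hours of the extra users.

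- All randomised, non-users at 0 h: (p_V − p_C) × e
- Users only: [p_C × m + (p_V − p_C) × e] / p_V − m

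First row worked: 0.15 × 3 = +0.45; (0.60 × 5 + 0.15 × 3) / 0.75 − 5 = 4.60 − 5 = −0.40.

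| Uptake, control / video | m (h) | e (h) | All randomised (h) | Users only (h) |
|---|---|---|---|---|
| 60% / 75% | 5 | 3 | +0.45 | −0.40 |
| 70% / 80% | 5 | 3 | +0.30 | −0.25 |
| 60% / 75% | 4.5 | 2 | +0.30 | −0.50 |
| 70% / 80% | 4.5 | 2 | +0.20 | −0.31 |
| 60% / 75% | 4.5 | 4.5 | +0.68 | 0.00 |
| 70% / 80% | 4.5 | 4.5 | +0.45 | 0.00 |
| 60% / 60% | 4.5 | none | 0.00 | 0.00 |

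For scale, 60% and 75% of 104 leave about 62 and 78 users. The users-only standard error is 2.5 × √(1/62.4 + 1/78) = 0.42 h.

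**4. Power once zeros are counted.** The protocol does not say whether its SD of 2.5 h includes patients with zero use. If it describes users only, and users average 4.5 h (assumed) with uptake p, the variance over all randomised is p × (2.5² + 4.5²) − (4.5p)². At p = 0.60 this is 0.60 × 26.5 − 2.7² = 8.61, so the SD is 2.93. Power for 1 h at 104 per arm is Φ(1 / (SD × √(2/104)) − 1.960).

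| Uptake | SD (h) | Total N for 80% power | Power at 208 |
|---|---|---|---|
| 60% | 2.93 | 272 | 69% |
| 70% | 2.94 | 272 | 69% |
| 80% | 2.87 | 260 | 71% |
| 90% | 2.73 | 234 | 75% |

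If 2.5 h already includes zero users, power at 208 stays at 82%.

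**5. If patients without a value are left out instead.** With SD 2.5 h, power at 208 randomised is 80.3% with 5% lost, 78.1% with 10% and 73.2% with 20%. This counts only the loss of numbers, not the selection in step 3.

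**The case against.** The strongest reply is that the protocol excludes nobody. It commits to intention-to-treat and sets the outcome in both arms, and a patient who never starts CPAP can naturally be scored 0 h. A reader might infer that the plan deliberately analyses users only; the text does not support that. What stands is narrower. The protocol supplies no value for these patients, its only stated source cannot produce one, and the methods may be settled after the data are seen.

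Second, missing-download rules and imputation commonly belong in a statistical analysis plan, which may exist. That is fair for the imputation details. What the primary endpoint equals for a randomised patient is part of its definition and belongs in the protocol.

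Third, non-attendance need not mean no data. The word *usually* leaves room for downloads outside the visit, and nothing in the documents shows that non-attenders are mostly non-users.

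Fourth, a reader might infer from Aims 1 and 2 that an as-treated comparison is planned. The videos are played in the laboratory that night and the next morning, so watched and allocated should nearly coincide. The phrase is most likely shorthand for the video arm.

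Fifth, a reader might take the change of sign as demonstrated. It depends on an uptake gain, on weaker extra users and on no effect in the others. At −0.40 h it is less than one standard error (0.42 h), so such a trial would more probably look null than harmful. The +0.45 h is also under half of the 1 h target.

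**Conclusion.** The concern holds in a limited form. The protocol does not define the primary outcome for randomised patients without a machine or a download, and its stated source and test would tend to produce a users-only comparison under an intention-to-treat label. That is a weakness in the endpoint definition, not a proven exclusion.

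Under the assumed inputs, the users-only estimate falls short of the all-randomised estimate by 0.45 h to 0.85 h wherever uptake differs. For example, 0.45 − (−0.40) = 0.85 and 0.45 − 0.00 = 0.45. These gaps are large against a 1 h target and enough to hide or reverse an effect made through uptake. If uptake is equal and the same kind of patient takes it up, this bias is absent. The power of 69% to 75% applies only if the 2.5 h SD describes users alone and users average 4.5 h.

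**What to change.** - Define the primary outcome for every randomised patient as metered hours divided by all nights in a fixed window before the visit. Enter 0 h where non-use is known: CPAP declined, never obtained or returned, and unused nights.
- Report hours among users only as supportive description.
- Treat unknown use (no download) separately as missing data, with a zero-hours sensitivity analysis. The imputation details can sit in the statistical analysis plan.
- State how patients who entered with suspected OSA and turn out not to be offered CPAP are counted, identically in both arms.
- Fix these rules before any comparison by arm, so that a later look at data quality cannot decide them.
- State whether the SD of 2.5 h includes zero users, and restate the power if it does not.
- As a minor tidy-up, reword Aims 1 and 2 to refer to patients allocated to the videos.

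The cost is mainly protocol wording and some extra data work. The downside is a lower mean, a larger SD and a less favourable stated power.
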